### 2.2 TREATMENT COMPARISONS

Study medications will not be blinded as this will not be practical. The effects of CAMPATH on the lymphocyte count are readily apparent, and are not shared with basiliximab. Also, the necessity of therapeutic drug level monitoring in the maintenance phase will make it infeasible to blind the tacrolimus and sirolimus.

#### 2.2.1 CAMPATH- vs basiliximab-based induction

At the time of surgery, patients will be allocated to receive either:

- CAMPATH induction, followed by low-dose tacrolimus (target trough levels 5-7 ng/mL) and MPA (360mg bd); or
- Basiliximab induction, followed by standard-dose tacrolimus (target trough levels 5-12 ng/mL), MPA (540 – 720mg bd) and reducing-dose corticosteroids (which will be withdrawn at the discretion of the local investigator[see Section 4.2.1.1]).

[figure not shown]
#### 2.2.2 Tacrolimus- vs sirolimus-based maintenance therapy

Six months after transplantation, patients will be allocated to receive:

- tacrolimus-based maintenance therapy (target trough level 5-7 ng/mL); or
- sirolimus-based maintenance therapy (target trough level 6-12 ng/mL for first six months, then reducing to 5-10 ng/mL). The study treatments are outlined below in figure 3. Further details of the treatment schedules are given in Appendix 2: Detailed treatment

---

 See footnote on page 10.

**Figure 3:** randomization scheme and timeline, including timing of primary assessment. For more detail of treatment schedules, see Appendix 2: Detailed treatment schedules. If mycophenolate sodium cannot be prescribed for local reasons, a dispensation can be made to allow mycophenolate mofetil to be substituted (see Appendix 9: Mycophenolate dosing for equivalent dosing).

schedules.

## 2.3 ASSESSMENT OF OUTCOMES

Two data analysis plans will be agreed by the Steering Committee. The first of these will describe detailed methods for the analysis of the comparison of the group allocated to CAMPATH induction with the group allocated to basiliximab induction. This will include the primary assessment of acute rejection at six months years. Comparisons at later time points may be possible, but they are potentially biased by the effect of the second randomisation.

The second will describe the detailed methods for the analysis of the comparison of the group of patients allocated to receive tacrolimus-based maintenance therapy with the group allocated to receive sirolimus-based maintenance therapy. This includes the primary assessment of graft function at two years, and secondary assessments of safety outcomes at one year.

### 2.3.1 *Comparison of induction therapies*

#### 2.3.1.1 Primary assessment at six months

The primary comparison will involve an “intention-to-treat” analysis of the time to first biopsy proven acute rejection episode, in patients allocated to arm 1 (CAMPATH induction) and arm 2 (basiliximab induction).

#### 2.3.1.2 Secondary assessments at six months

Secondary assessments will include “intention-to-treat” analyses of:

- all rejection episodes (biopsy-proven and presumed)
- steroid-resistant rejection
- delayed graft function
- safety measures e.g. incidence of serious infection
- graft and patient survival

#### 2.3.1.3 Tertiary assessments at two and five years

The long-term effect of induction therapy will be assessed in terms of:

- graft outcomes: graft function and graft survival
- safety outcomes: incidence of serious infection and cancer
- other outcomes of interest including major vascular events (a composite outcome of non-fatal myocardial infarction, cardiac death, non-fatal or fatal stroke and arterial revascularisation)
- patient survival

Because such analyses are potentially biased by unequal numbers of patients undergoing the second randomization in the two induction therapy arms, these tertiary assessments will be interpreted cautiously and substantial allowance will be made for multiple hypothesis testing, the nature of the events and evidence from other studies.

### 2.3.2 *Comparison of maintenance therapies*

#### 2.3.2.1 Primary assessment at two years

The primary comparison will involve an “intention-to-treat” analysis of the graft function (estimated by calculating GFR using the 4-variable MDRD [Modification of Diet in Renal Disease] equation) at two years after transplantation, in patients allocated to sirolimus-based maintenance therapy (arms 1a and 2a) and tacrolimus-based maintenance therapy (arms 1b and 2b).

#### 2.3.2.2 Secondary assessments at two and five years

All secondary assessments will be conducted amongst all patients entering the maintenance therapy randomisation, and will be of the effects of maintenance treatment allocation (tacrolimus- versus sirolimus-based therapy) on safety outcomes and efficacy measures:

1. safety measures
  - incidence of serious infections (see section 4.1 for definition);
  - incidence of malignancy (including post-transplantation lymphoproliferative disorder);
2. efficacy measures
  - incidence of acute rejection (biopsy-proven, presumed and steroid resistant: see Appendix 1: Definitions for definition);
  - graft survival;
  - patient survival.
  - major vascular events (a composite outcome of non-fatal myocardial infarction, cardiac death, non-fatal or fatal stroke and arterial revascularisation)

#### 2.3.2.3 Tertiary assessments at five years

In addition, some of the above comparisons will also be conducted in pre-specified sub-groups of patients, including:

- induction therapy allocation;
- men and women;
- cadaveric and living-related transplants;
- categories of HLA mismatch;
- white and non-white;
- first transplant and subsequent transplants;
- categories of sensitisation;
- categories of baseline graft function (eGFR <40, 40-60, >60 mL/min/1.73m^2);
- categories of baseline proteinuria (<30, 30-300, >300-1000, >1000 mg/day).

### 2.3.3 *Safety analysis at one year*

The relevant safety data from the induction therapy comparison at six months and the maintenance therapy comparison at one year will be included in this early safety analysis, once all patients have completed one year of follow-up.

### 2.3.4 *Health Economic analysis*

An economic analysis will be performed, with the objective of estimating average costs and effectiveness within each study arm, and the incremental cost-effectiveness of CAMPATH induction compared to basiliximab induction, and of tacrolimus-based maintenance therapy compared to

sirolimus-based maintenance therapy. The analyses will be performed primarily from a health service perspective, but additional information will be collected on employment status.

The time-horizon for the first comparison will be 6 months, in line with the primary trial outcomes, to include any differences in acute rejection rates but exclude any effects from the second randomisation. The time horizon for the second comparison will be at 2 years. In both cases additional lifetime analyses will be performed, based on registry data and an extrapolation model; this will be important to capture the long-term costs and effectiveness of the interventions and spill-over effects including the effect of reduced acute rejection rates and improved longer-term graft function on the availability of organs for others on waiting lists.

Costs will be based on measured resources used and appropriate national unit costs. Resources will include immunosuppressant and other drugs, nephrology out-patient visits, biopsies and tests, and all treatments related to adverse events. These will be obtained primarily from trial case report forms, including (from one year after transplantation) a simple 1-page questionnaire to patients requesting information on GP and other consultations, other health care use, days off work and current work status.

Outcomes in the economic evaluation will be based on quality adjusted survival. Quality of life will be measured using the EQ-5D administered at the discharge visit (for retrospective assessment of quality of life prior to transplant, and then at 3, 6, 9 and 12 months and annually thereafter).

## **2.4 DURATION AND DEFINITION OF END OF STUDY**

Patients will be recruited into the study at the time of their kidney transplant surgery. All willing and able patients will be seen then, and at the time of their discharge from hospital after this index admission. The patients will be seen again at 1, 3, 6, 9 and 12 months after surgery: these visits will usually be scheduled to coincide with their routine clinical appointments. Following this, patients will be followed up by annual postal or web-based questionnaires until a median follow-up of five years. Patients who do not respond to two mail or e-mail requests for information will be contacted by telephone by a member of the 3C study team in order to complete the questionnaire. Patients will also be "flagged" with central registries (e.g. NHS Information Centre, UK Renal Registry, Scottish Renal Registry, Hospital Episode Statistics) for long-term follow-up (i.e. beyond the period of questionnaire follow-up and potentially for the lifetime of the patient) which will permit a reliable assessment of the long-term safety and efficacy of the study treatments. The study will therefore continue until all patients have died (or withdrawn consent for registry-based follow-up).

## **2.5 SAMPLE SIZE CALCULATIONS**

The 3C study sample size is determined by the maintenance therapy allocation. A meta-analysis of the effect of conversion to sirolimus-based maintenance therapy showed an improvement in eGFR of 6.4 mL/min (95% CI 1.9-11) in the group assigned to sirolimus (12). The trials included in this meta-analysis varied in duration, with most patients followed for one year. If these differences could be maintained, it would be reasonable to anticipate a 10 mL/min difference in GFR two years after conversion to sirolimus (i.e. median follow-up at least 2.5 years after transplantation). Adherence to sirolimus therapy is likely to be around 75% (i.e. approximately 25% of patients allocated sirolimus in randomised trials discontinue it (12)) and this must be taken into consideration.

800 patients would have excellent power (>90%) with  $\alpha = 0.05$  and good power (>80%) with  $\alpha = 0.01$  to detect such a difference when allowance is made for the likely proportion of patients who are ineligible for the second randomisation and adherence with sirolimus.

800 patients would also provide good power (90%) with  $\alpha = 0.05$  to detect a halving in the acute rejection rate at six months (from 15% to 7.5%), which is the primary comparison in the induction therapy comparison.

## 2.6 DATA AND SAFETY MONITORING

### 2.6.1 *Interim analyses: role of the Data Monitoring Committee and Steering Committee*

During the period of the study, interim analysis of serious adverse events, particularly those believed to be due to study treatment, will be supplied regularly (every three months during the first year of the study and six-monthly thereafter) in strict confidence to the Chairman of the independent Data Monitoring Committee. In the light of these analyses and the results of other relevant trials, the Data Monitoring Committee will advise the Steering Committee if, in their view, the randomised comparisons in the 3C trial have provided **both** (i) “proof beyond reasonable doubt” that for all, or some specific types, of patient, induction with CAMPATH and/or maintenance therapy with sirolimus is clearly indicated or contraindicated in terms of a net difference in graft or patient survival; **and** (ii) evidence that might be reasonably expected to influence materially the patient management of many clinicians who are already aware of the main results of any other trials. The Steering Committee can then decide whether to modify the study, or to seek additional data. Unless this happens, the Steering Committee, the local lead investigators, the study participants, and all study staff (except those who provide the confidential analyses to the Data Monitoring Committee) will remain blind to the study results.

## 2.7 CENTRAL COORDINATION OF LOCAL CLINICAL CENTRES (HOSPITAL CLINICS)

### 2.7.1 *Overview of study organisation*

The 3C Trial will be coordinated by the Coordinating Centre based at the Clinical Trial Service Unit of Oxford University. The Coordinating Centre will be responsible for the administrative support of the Local Clinical Centres (LCCs). At each LCC, a Lead Investigator (a transplant surgeon or nephrologist) and a LCC Research Nurse (or, in some circumstances, medically qualified research fellow) will be responsible for the identification, recruitment and follow-up of study patients for the duration of the study. It is hoped that most of the transplant centres in the UK (23 currently) will participate.

### 2.7.2 *Training and monitoring*

The 3C Trial will be conducted in accordance with the principles of the International Conference on Harmonisation Guidelines for Good Clinical Practice (ICH-GCP) and relevant local, national and international regulations. Prior to initiation of the study at any LCC, the LCC clinic staff will be trained in the methods of the study and the LCC may be visited by a representative of the Coordinating Centre to ensure that the site has adequate facilities and resources to carry out the study. In addition, LCC Lead Investigators and LCC clinic staff will be provided with materials detailing relevant study procedures for LCCs (“Manual for Local Clinical Centre Procedures”).

---

 appropriate criteria of proof beyond reasonable doubt cannot be specified precisely, but in general terms a difference of at least three standard deviations in an interim analysis of graft or patient survival would be needed to justify halting, or modifying the study prematurely. This criterion has the practical advantage that the exact number of interim analyses is of little importance.

During the study, representatives of the Coordinating Centre will visit all LCCs as required by needs of the centre and monitoring. The purpose of these visits will be to help LCC clinic staff to resolve any local problems with the study, to ensure that the study is conducted according to the protocol and Good Clinical Practice, and to review study records, data quality and the completeness of follow-up. A report of each visit will be prepared by the monitor and reviewed by the Coordinating Centre staff.

#### *2.7.3 Supply of study materials*

Equipment for the study clinics and all paperwork (e.g. study manuals, stationery) will be provided by the Coordinating Centre. Study treatments will not be provided (see section 3.13).

#### *2.7.4 Data management*

Patient data will be entered by clinic staff onto electronic Case Report Forms, which will then be forwarded to the coordinating centre. Data from these forms will be entered into computer databases at the coordinating centre, and stored on secure servers. Patient identifiable details will be stored for the purposes of flagging patients with central registries, but such details will be stored separately to all other data collected and linked by a unique study identifier.

#### *2.7.5 Laboratory measurement of samples*

All blood and urine test results required for the 3C study will coincide with those taken for routine clinical management. The Case Report Forms will include spaces for relevant results to be transcribed.

#### *2.7.6 Source documents and archiving*

As far as possible the CRF will be completed by direct interview with the participant. It may also be necessary to refer to the patient's hospital records (including electronic clinical, laboratory and pharmacy records). Furthermore, the additional information obtained on key variables from electronic records, reported outcome measures and other relevant events, death certificates and other information from national registries will also be source documents for the study. Investigators will permit trial related monitoring, audit or regulatory inspection providing direct access to source data/documents.

#### *2.7.7 Funding*

This study has been initiated and designed by the 3C Trial Steering Committee, and the data will be collected, analysed and published independently of the source of funding. Grants have been received from NHS Blood & Transplant, Novartis Pharmaceuticals UK Ltd and John Wyeth and Brother Ltd. The University of Oxford will act as the Sponsor in this study. This grant will support the central and local administration of the study, meetings and travel, study materials, and the necessary LCC clinic staff time. The cost of drugs (including study drugs) will not be funded by the 3C budget.

#### *2.7.8 Indemnity*

The University of Oxford, as Sponsor, will indemnify participating Research Subjects against any harm arising from their participation in this study. Furthermore, any harm arising from the provision of clinical treatment - and which would have arisen irrespective of the participation in this study - , and arising from negligence will be indemnified under the terms of the participating hospital trust's membership of Clinical Negligence Scheme for Trusts [or local variations for any hospitals participating from Scotland, Wales or Northern Ireland] administered by the NHS Litigation Authority.

*2.7.9 Publications, reports and substudies*

Draft copies of any manuscripts will be provided to all local lead investigators for review prior to their submission for publication. Papers will be written in the name of the 3C Trial Collaboration, with each individual investigator named personally at the end of the report (or to comply with medical journal requirements, in web-based material posted with the report).

Proposals for sub-studies on patients randomised into the 3C Trial will be welcomed, but must be approved by the Steering Committee before these begin. In considering such proposals, the Steering Committee will need to be satisfied that the proposed sub-study is of a high quality and that it will not compromise the main study in any way (for example by reducing the recruitment rate or compliance with study treatment).

### 3 SUMMARY OF PRACTICAL PROCEDURES

#### POTENTIALLY ELIGIBLE

- ↓
- active on transplant waiting list, or live donor transplant planned
  - aged over 18
  - male or female

#### IDENTIFICATION AND INVITATION

- ↓
- potentially eligible patients identified from local transplant waiting list
  - agreement to screen such patients sought from consultants
  - patient sent information about the trial

#### FIRST RANDOMISATION (prior to surgery)

- ↓
- Written informed consent sought from eligible and willing patients
  - Basic medical history and details of transplant recorded
  - induction therapy randomisation: CAMPATH- or basiliximab-based induction
  - Inform patient's nephrologist, transplant surgeon and GP of randomisation

#### DISCHARGE VISIT (and FOLLOW-UP VISITS at 1, 3, 6, 9 & 12 months)

- ↓
- Further details of medical history and transplant
  - Serious adverse events
  - Current medication
  - Clinical measurements and laboratory results

#### SECOND RANDOMISATION (at ~6 months after transplantation)

- ↓
- check inclusion and exclusion criteria for second randomisation
  - maintenance therapy randomisation: sirolimus- or tacrolimus-based maintenance therapy
  - inform patient's nephrologist, transplant surgeon and GP of randomisation

#### FOLLOW-UP after one year after transplantation

- ↓
- Annual postal questionnaire for serious adverse events, medications, other health care usage and quality of life (until median 5 year follow-up)
  - Registry sources for laboratory results, survival and cancers (for duration of the study).

#### MONITORING OF SAFETY AND EFFICACY

- ↓
- Central review of blood results and SAEs by Coordinating Centre
  - Further details on relevant outcomes from hospital records sought by LCC clinic staff
  - Relevant events confirmed and reviewed by central Outcomes Adjudication Panel

See also Appendix 6: Schedule of study procedures.

### 3.1 ELIGIBILITY FOR THE 3C STUDY

Patients are eligible for randomisation into the 3C Study if: (a) their nephrologist or transplant surgeon does not believe there is a definite indication for, or contraindication to, CAMPATH or sirolimus; and (b) all inclusion criteria are satisfied whilst no exclusion criterion applies.

#### 3.1.1 *Identification of potentially eligible patients*

Potentially eligible patients will be identified by the LCCs from their transplant waiting list with their consultant's permission. Such patients will be sent a letter informing them of the trial or informed at routine outpatient clinic attendance (at centres where mailing everyone on the local waiting list is not feasible or desirable). Details of the 3C study will be provided with contact details for the local clinic staff should the patient have any questions. This will raise knowledge and awareness of the trial so that, when the patient is approached in the immediate pre-operative period, informed consent can more appropriately be requested.

### 3.2 FIRST RANDOMISATION VISIT

#### 3.2.1 *Assessment of relevant medical history and eligibility*

This will be done after the patient has been called for transplant. If this is during the time when the clinic staff are working, they will discuss the trial with the patient. If it is outside of these hours, then the local lead investigator (or his/her designated deputy) will undertake this discussion.

There is no contraindication to entry into the 3C study on the basis of concomitant medication. All medications will be recorded at the discharge visit (see section 3.3.3 below).

#### 3.2.1.1 Inclusion criteria for first randomisation

- men or women aged over 18 years;
- recipient of a first or subsequent kidney from a cadaveric or live donor;
- negative pregnancy test at randomisation, and agreement to use an acceptable form of contraception for duration of the study from women with child-bearing potential. Anuric (therefore unable to provide a urine specimen) female patients with child-bearing potential will be eligible, providing they agree to use an acceptable form of contraception.

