#### 3.2.1.2 Exclusion criteria for first randomisation

- Recipients of multi-organ transplants (eg kidney + liver, kidney + pancreas)
- previous treatment with CAMPATH;
- active infection, including HIV (antigen or antibody), hepatitis B (surface antigen), or hepatitis C (PCR) positivity;
- past history of anaphylaxis following exposure to humanised monoclonal antibodies;
- history of malignancy (with the exception of adequately treated non-melanoma skin cancer) diagnosed or recurred in the last five years;
- loss of previous kidney transplant within six months not due to technical reasons;
- medical history that might limit the individual's ability to take trial treatments for the duration of the study.

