## 3.8 DISCONTINUATION OF STUDY TREATMENT

Patients will be encouraged to adhere to study treatments during the study. However, the local investigator may decide to discontinue study treatment at any time in the interests of the patient's health and well being. For example, study treatment may be temporarily or permanently discontinued for a particular patient if one of the following criteria are met:

- **serious** adverse event **thought likely to be due to study treatment**;
- conditions or procedures in which trial agents may be contraindicated (e.g. patients on sirolimus undergoing surgery where wound healing is a concern) (see section 4.3.1.1);
- pregnancy or any other situation where, in the opinion of the patient's own doctors or the clinic staff, continuing study treatments would not be in the patient's best interest.

If a patient wishes to discontinue from study treatment, he or she would still be followed-up for the duration of the study in the usual way. Complete follow-up of such data is essential as the analysis will be on an “intention-to-treat” basis.

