**Cautions/Side Effects:**

Exercise caution in the handling and preparation of the solution. Gloves must be worn. There is no information relating to the use of CAMPATH in pregnancy. As a precaution the company recommend it should not be handled by women who are pregnant or planning pregnancy. However the use of gloves will ensure there is no drug contact to staff. Safety glasses should be worn to avoid exposure in case of breakage or spillage.

Side-effects common with the first dose and include fever, rigors, headache, nausea, vomiting, rash, urticaria, pruritis, dyspnoea, hypotension and diarrhoea. Infusion related fever commonly begins 5-6 hours after infusion starts. More severe reactions such as bronchospasm and severe hypotension have been seen in a few instances and late hypotension can occasionally be a problem.

Thrombocytopenia most common during weeks 2-4 and neutropenia common between weeks 4-8.

*Treatment of side-effects:*

Side effects can be controlled by slowing or temporarily stopping the infusion. Administer PRN medication (paracetamol PO, chlorphenamine IV, hydrocortisone IV) if necessary.

Nebulised salbutamol may be required for bronchospasm.

If hypotension develops, hydration with normal saline is indicated, unless contraindicated based on underlying cardiac status.

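### Anuric women of child-bearing potential can be randomised to study treatment without any test that excludes a current pregnancy

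*Protocol*

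**What the plan says.** The inclusion criteria for the first randomisation (Protocol 3.2.1.1) set two conditions together: "negative pregnancy test at randomisation, and agreement to use an acceptable form of contraception for duration of the study from women with child-bearing potential". The type of specimen is not stated.

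The following sentence treats one group differently: "Anuric (therefore unable to provide a urine specimen) female patients with child-bearing potential will be eligible". The proviso attached to this exception reads: "providing they agree to use an acceptable form of contraception". Of the two conditions, only the contraception agreement is kept for them. The bracketed remark about urine is the only reason offered.

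Three other places bear on the point:

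- Section 4.8.1 (Cautions/Side Effects) says: "There is no information relating to the use of CAMPATH in pregnancy".
- Section 3.8 lists, among examples of when study treatment may be interrupted or ended, "pregnancy or any other situation where, in the opinion of the patient's own doctors or the clinic staff", continuing would not serve the patient.
- Section 3.10.2 counts a birth defect after maternal exposure as a serious adverse event.

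The SAP does not mention pregnancy.

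**The concern.** The two conditions in the general criterion do different work. The test addresses whether a woman is pregnant on the day; the contraception agreement addresses whether she may become pregnant later. Dropping the test and keeping the agreement leaves the first question unanswered.

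The stated reason also covers less than the exception does. Lack of urine rules out one specimen type, while the criterion itself asks only for a pregnancy test. Unless no other specimen can be used, anuria explains why a urine test is not done, but not why no test is done.

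At stake is the safety of a participant and a fetus, in a subgroup picked out by a practical obstacle and not by lower risk. Induction treatment is given around surgery (section 4.2.1), so a pregnancy recognised afterwards has already been exposed to it.

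**Working it through.** No figure in the plan needs to be reproduced. The check is whether any other provision would exclude an unrecognised pregnancy in an anuric woman before she is randomised.

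1. **Inclusion criteria (3.2.1.1).** If the test still applied to anuric women, the second sentence would have no function. The protocol does not use the word waiver, but that is the plain reading.
2. **Exclusion criteria (3.2.1.2).** Seven are listed, and pregnancy is not among them. The last, on medical history that might limit the taking of trial treatment, can act only on what is already known.
3. **General eligibility (3.1).** The responsible nephrologist or surgeon must see no definite contraindication to CAMPATH or sirolimus. This covers a known or suspected pregnancy, not an unrecognised one.
4. **Second randomisation (3.5).** The two listed exclusions concern proteinuria and recent rejection. A check at that stage would in any case come 5 to 7 months after transplantation.
5. **Schedule of procedures (Appendix 6).** No pregnancy test is listed at any visit, for any participant.

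None of these closes the gap.

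Next, which treatment would be received. All women enter the same first randomisation, to CAMPATH or basiliximab (section 2.2.1), and both arms then receive tacrolimus and mycophenolate. The untested exposure is therefore to study treatment in either arm. CAMPATH is the only study drug on whose use in pregnancy the protocol itself comments.

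Finally, whether lack of urine makes testing impossible. One exclusion already depends on viral markers: "active infection, including HIV (antigen or antibody), hepatitis B (surface antigen), or hepatitis C (PCR) positivity". Antibody and antigen status suggests that blood results are used for eligibility, although the protocol does not say these are obtained on the day. That a pregnancy test can be run on blood is general knowledge and is not stated in the documents.

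**Size.** The number affected would be the number randomised, times the share who are women of child-bearing potential, times the share of those who are anuric. The first term is planned at 800 (section 2.1). The documents give neither share and no pregnancy rate, so no count can be derived.

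**The case against.** The strongest reply is that this is a deliberate exception and not an oversight: the protocol states a rule, names a group to which part of it does not apply, and gives a reason. Eligibility is assessed after the patient has been called for transplant, sometimes outside working hours (section 3.2.1), when a further result may be slow to obtain. No passage mentions a blood pregnancy test, its turnaround, or its performance in end-stage renal failure. Clinician judgement under section 3.1 applies to every patient.

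Part of this stands. The availability and speed of a blood test are assumptions, and clinician judgement narrows the gap. But the protocol does not give urgency as its reason, and the exception also covers live-donor transplants, which section 3 describes as planned. Judgement cannot act on a pregnancy nobody has recognised.

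A reader might also infer more than the documents support:

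- **That the protocol contradicts itself on handling.** Section 4.8.1 reports of CAMPATH that "As a precaution the company recommend it should not be handled by women who are pregnant or planning pregnancy". This is a manufacturer's precaution for staff, followed by a statement that gloves prevent contact. It sets no standard for patient eligibility.
- **That section 3.8 conflicts with the entry rule.** Its reference to pregnancy is an example within a discretionary clause about treatment already under way.
- **That the problem is confined to CAMPATH.** The same women may be allocated basiliximab, and both arms share the other drugs.
- **That many women are affected.** No passage says how common anuria is among those eligible.

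**Conclusion.** The point holds as a participant-safety gap in the eligibility criteria. As written, an anuric woman of child-bearing potential can be randomised to either induction arm with a current pregnancy not excluded, and the reason given does not justify the absence of any test.

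Its size cannot be estimated from the documents. I assume that few pregnancies would occur in this group; the case for change rests on how serious the harm would be and not on its frequency. There is no effect on power, alpha or the intention-to-treat comparisons.

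The conclusion rests on reading the exception as removing the test, which is the only reading that gives the sentence a purpose, and on no substitute check being required elsewhere in the protocol. The remedy further assumes that a blood test can be obtained before randomisation. If the sponsor finds that it cannot, the exception needs a stated justification beyond the lack of urine.

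**What to change.** Reconcile the exception in section 3.2.1.1 with the requirement in the same bullet, so that one testing criterion applies to every woman of child-bearing potential. Suggested wording: *negative pregnancy test (urine, or blood where no urine can be provided) at randomisation*, with the contraception agreement kept as it is. Align the eligibility form.

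The cost is one amended sentence, one form change and one assay for a small subgroup. The downside is a possible short wait before randomisation, sometimes out of hours. The sponsor should confirm with the centres that a blood test is available, and how quickly it can be reported, before adopting the wording.
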